A computer-generated random allocation using a randomly permutated block design (10-patients per block) will be utilized. Randomization will be performed at the start of the study with study group assignments placed in sealed nontransparent envelopes. The envelopes will be numbered in order. The next envelope in numerical order will be brought to the operating room where it will be opened by a participating surgeon and another operating room staff member. Both personnel will sign the envelope to validate that proper envelope opening and interpretation were performed. The envelopes will then be collected for record keeping. This procedure will help to minimize surgeon bias as it is impossible for surgeons to be masked to the randomization. Participants and research staff will be masked during the study as much as possible, however there will be a description of the type of sacrospinous ligament fixation device used within the body of the operative note for each patient that research staff could gain access to. Intraoperative data, including any adverse event that may unmask the study coordinators, will be reported by the surgeon directly to the study administrators.

STUDY INTERVENTION

The primary intervention is sacrospinous fixation utilizing either the Anchorsure® system or the Capio[™] Slim device. Concomitant anterior and/or posterior colporrhaphy (plication of fibromuscular vaginal tissue), enterocele repairs, transvaginal hysterectomy, bilateral salpingo-oophorectomy, perineoplasty, midurethral sling procedures, or other procedures not involving the pelvis, anus, buttock, or lower extremities may be performed. Prolapse procedures will be recorded but not controlled by study protocol. Participating surgeons are all extensively experienced in sacrospinous ligament fixation. Any use of allograft, xenograft, or synthetic graft material for POP repair will not be permitted.

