All AEs must be recorded on the AE CRF supplied by the study coordinator, entered into the site AE log, and then entered into REDCap. Each AE will be sequentially numbered according to patient. For example, patient 008's first AE would be 008.01. The principal investigator will determine the relationship of the AE to the operative procedures, the relationship of the AE to the device, along with the severity of each reportable AEs. All complications will be adjudicated by a Co-Investigator assigning DINDO scores. The adjudicating Co-Investigator will also determine if the complications are more likely to be related to the overall surgery, sacrospinous ligament fixation surgery or both. Complications that are deemed not related to the surgery will be excluded (such as, a carpal tunnel syndrome exacerbation at 6 weeks post-operation).

Severe AEs (SAEs) must be reviewed by the PI within two business days.

TABLE 1. Classification of Surgical Complications DINDO Grade Definition

Grade 1	Any deviation from the normal postoperative course without the need for pharmacologic treatment. Allowed therapeutic interventions are: drugs as antiemetics, antipyretics, analgesics, physiotherapy
Grade II	Requiring pharmacological treatment with drugs other than such allowed for grade I complications. Blood transfusions and total parenteral nutrition are also included
Grade III	Requiring surgical, endoscopic or radiological intervention
IIIA	 Intervention not under general anesthesia
IIIB	- Intervention under general anesthesia
Grade IV	Life-threatening complication (including CNS
	complications)* requiring IC/ICU management
IVA	 Single organ dysfunction (including dialysis)
IVB	- Multi-organ dysfunction
Grade V	Death

Reportable AEs include those determined to be related to the operative procedures or the device as listed below:

Intraoperative complications attributable to sacrospinous ligament fixation:

- Pelvic hemorrhage
- Buttock pain or posterior thigh pain on a side with a sacrospinous ligament fixation
- Lower extremity impaired sensation on a side with a sacrospinous ligament fixation
- New neurologic conditions in the lower extremity on a side with a sacrospinous ligament fixation
- Rectal or bladder injury during dissection or placement of sacrospinous ligament sutures
- Avulsion/loss of bullet on Capio[™] device

Postoperative complications:

Infection requiring antibiotics

- Cardiac or myocardial infarction
- New neurologic conditions

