- New pulmonary conditions
- Pelvic abscess
- Blood transfusion
- Venous thromboembolism
- Hospital readmissions
- Emergency room evaluations
- Unplanned clinic visit
- Leg pain or difficulty ambulating on a side of the body without a sacrospinous ligament fixation
- Pelvic fistulas involving the vagina, bladder, or bowels
- Reoperations including repeat prolapse surgery

Please note that underlying diseases are not reportable as AEs unless there is an increase of severity or frequency during the course of the study that is directly attributable to the surgical intervention. If an AE has not resolved at the time of AE Form completion, the form will be saved as incomplete in REDCap until resolved. Once the AE is resolved, the AE form will be updated, saved as complete, and entered into REDCap.

Adverse Event Definitions

Adverse Event: any untoward medical occurrence, unintended disease or injury, or any untoward clinical signs (including abnormal laboratory finding) in subjects, whether or not related to the operative procedures

Serious Adverse Event: an adverse event that:

- Led to death
- Led to serious deterioration in the health of the subject that either resulted in
 - o a life-threatening illness or injury
 - o a permanent impairment of a body structure or a body function
 - in-subject or prolonged hospitalization of existing hospitalization
 - medical or surgical intervention to prevent life-threatening illness or injury or permanent impairment to a body structure or a body function
- Led to fetal distress, fetal death or a congenital abnormality or birth defect

Relationship of AE to Operative Procedures:

- Unrelated: No evidence that the timing of the AE has a relationship to the operative procedures performed.
- Possibly Related: The AE has a timely relationship to the operative procedures performed, however a potential alternative etiology may be responsible for the AE.
- Probably Related: The AE has a timely relationship to the operative procedures performed and the causative relationship can clearly be established. No potential alternative etiology is apparent.

Relationship of AE to Device:

- Unrelated: No evidence that the timing of the AE has a relationship to the device placement.
- Possibly Related: The AE has a timely relationship to the device placement, however a potential alternative etiology may be responsible for the AE.

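### Complications judged unrelated to surgery are excluded, without saying from what or that the judges are masked, so the adverse event comparison may rest on an unmasked judgement made after randomisation

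*Combined protocol and SAP*

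**What the plan says.** **Recording and definition.** Reporting Adverse Events sends every AE to the case report form, the site log and REDCap. Adverse Event Definitions covers any untoward occurrence, "whether or not related to the operative procedures".

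**Exclusion.** Reporting Adverse Events then says: "Complications that are deemed not related to the surgery will be excluded". Its example is a flare of carpal tunnel syndrome at six weeks. The same section adds a second limit: "Reportable AEs include those determined to be related to the operative procedures or the device as listed below".

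**Who judges.** Two roles are named. "The principal investigator will determine the relationship of the AE to the operative procedures, the relationship of the AE to the device", and also the severity. Separately, "All complications will be adjudicated by a Co-Investigator assigning DINDO scores", and that person also decides whether a complication belongs to the overall surgery, to the sacrospinous fixation or to both.

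**Masking.** Randomization and Masking says "it is impossible for surgeons to be masked to the randomization". For others, "Participants and research staff will be masked during the study as much as possible", with the caveat that "there will be a description of the type of sacrospinous ligament fixation device used within the body of the operative note". Events that could unmask the study coordinators go from the surgeon straight to the study administrators. The adjudicator is not mentioned.

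**Analysis.** Clinical outcomes treats adverse events as a dichotomous secondary outcome, compared by chi-square, and says all of them will be reported by Dindo grade. No comparison of all recorded events is separately specified.

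**The concern.** Randomisation protects a comparison of everything that happened to the patients in each arm. It does not protect a comparison of events that have passed a filter applied afterwards by someone who may know the device. If an event in one arm is more readily attributed to something other than the operation than the same event in the other arm, a difference can appear or disappear without any difference between the devices.

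Many entries on the plan's own list need judgement: unplanned clinic visits, emergency room evaluations, new neurologic conditions, and leg pain on the side without a fixation. The stake is the safety comparison. It is secondary, but the background section says that improved safety could ultimately change standard technique.

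**Working it through.** **1. Setting the passages side by side.**

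| Question | What the plan gives |
|---|---|
| Which events are recorded? | All, related or not |
| Which are excluded? | Those deemed unrelated to the surgery |
| Excluded from what? | Not stated |
| Who decides? | The principal investigator judges relatedness to procedure and device. A Co-Investigator attributes complications to surgery, fixation or both, with no stated option for neither. No rule covers disagreement |
| Are they masked, or non-operating? | Not stated for either role |
| Can the device be learned? | Yes, from the operative note. One listed event, loss of the bullet on the Capio device, identifies the arm |
| Is an unfiltered comparison planned? | Not separately specified |

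If the exclusion applies to the analysis, the chi-square test is run on filtered events.

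**2. Size, by illustration.** The plan states no figure for the adverse event comparison, so there is none to reproduce. Inputs from the documents are n = 24 per arm (Power Calculation), the chi-square test (Clinical outcomes) and a two-sided 5% level (stated for the primary test and carried over here). Assumptions are a true event rate p equal in both arms, a proportion e of patients with events recoded as event-free in one arm only, and a Pearson chi-square without continuity correction.

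With a and b patients with events in the two arms and s = a + b:

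X² = (a − b)² × 2n / [s × (2n − s)], rejecting when X² ≥ 3.841.

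The rejection rate is the sum, over all a and b that reject, of Bin(a; n, p) × Bin(b; n, p(1 − e)). The false difference created is p × e; at p = 40% and e = 25% it is 0.40 × 0.25 = 10 points.

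| True rate, both arms | e = 0 | e = 10% | e = 25% | e = 50% |
|---|---|---|---|---|
| 20% | 5.4% | 5.7% | 7.8% | 16.7% |
| 40% | 5.5% | 6.4% | 11.6% | 33.3% |
| 60% | 5.5% | 7.9% | 20.1% | 59.0% |

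At a 40% rate the false differences are 4, 10 and 20 points. With 21 per arm, the evaluable number in the power calculation, the 40% row becomes 5.0%, 6.0%, 11.0% and 31.1%.

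A small one-sided exclusion therefore does little to the error rate at this sample size, and a large one matters. The estimated difference shifts in either case.

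**The case against.** The other side has several good points.

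- **Nothing is lost.** A reader might infer that unrelated events are dropped from the data. They are not: all AEs reach REDCap, and the text does not say that the exclusion applies to the chi-square comparison. This stands, which is why the conclusion is conditional.
- **The filter is relation to surgery, not to device.** Both arms have the same type of operation, and device relatedness is a separate judgement. A reader might infer that events are excluded for being unrelated to one device; the exclusion sentence does not say so. The route from knowing the device to excluding an event is therefore indirect, but not closed.
- **Discretion is limited.** Unrelated is defined as no evidence of a relationship in timing. An event with a timely relationship and a possible alternative cause is classed as possibly related, so on the plan's definition it is not unrelated. Within six weeks of surgery this leaves limited room. It narrows the concern without removing it.
- **The main outcomes are little exposed.** The primary pain score is patient-reported and bypasses adjudication. The intraoperative items listed under Specific Aim 2 (suture or anchor replacement, hemorrhage needing intervention or transfusion, equipment malfunction) are concrete and plainly surgical.
- **Masking is unstated, not absent.** A reader might infer that the adjudicator is unmasked. The documents support only that this person may be.

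It is also tempting to argue that a few judgements decide the result. At 24 per arm, 4 v 4 becoming 4 v 0 gives X² = 16 × 48 / (4 × 44) = 4.36, p = 0.037; 6 v 6 becoming 6 v 1 gives X² = 25 × 48 / (7 × 41) = 4.18, p = 0.041. The arithmetic is right, but these cases discard all four, or five of six, of one arm's events and none of the other's. No rate in the documents supports that. Fisher's exact test gives 0.11 and 0.10, so crossing 0.05 also depends on using chi-square with small counts.

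**Conclusion.** The concern holds in conditional form. The plan states an exclusion based on judged relatedness, does not say what it applies to, and does not say that either judge is masked or did not operate. If it applies to the adverse event comparison, that secondary comparison depends on a possibly unmasked judgement made after randomisation.

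The size of any bias cannot be taken from the documents. Under the assumptions above, with a 40% event rate and 24 per arm, false rejection moves from about 5.5% to 6.4%, 11.6% or 33.3% for one-sided exclusion of 10%, 25% or 50%. These figures show sensitivity and do not predict what will happen. The documents do not support a claim that biased adjudication is occurring or likely. The change is still worth making because the data needed are already collected.

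**What to change.** In Reporting Adverse Events, replace the exclusion with a main table comparing all recorded AEs by arm, whatever the relatedness, and show surgery-related events as a subset table. Point the chi-square comparison in Clinical outcomes to the main table.

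Where feasible, have relatedness and Dindo grade assigned by a co-investigator who did not perform that operation, from narratives with the device name removed. The documents do not say how many co-investigators there are or which of them operate, so availability needs checking. Device-specific events such as loss of the Capio bullet cannot be masked, and the text should accept this. It should also say whose relatedness judgement is used when the two roles disagree.

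The cost is one extra table, some redaction time, and some dilution of the main table by events that have nothing to do with the surgery; the subset table answers the last point. No new data or patients are needed.
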